7.3. Safety Analyses

Safety analyses will be performed using the Safety Analysis Set.

Safety analyses will include all AEs, ECGs, clinical laboratory data, physical examinations, and vital sign measurements using descriptive statistics.

No inferential statistical analyses are planned for the safety parameters of this study.

7.3.1. Study Duration, Treatment Compliance, and Exposure

Study duration will be summarized for all enrolled participants by cohort and overall. Study duration is defined as the time from first dose to the EOS or study discontinuation date (whichever occurs first) + 1.

Compliance during the Inpatient and Outpatient periods will be determined as the days taken / the days expected to be taken during active study treatment x 100. Treatment compliance will be summarized using descriptive statistics within cohort and overall. If a subject prematurely discontinues, his or her compliance will be based on the period up to the point of discontinuation from the study. Compliance will also be summarized using counts and percentages by compliance category (ie, $\geq 100\%$ compliance, 80 to $<100\%$ compliance, 60 to $<80\%$ compliance, etc.). A supporting listing will also be produced.

Exposure will be summarized for the Safety Set by cohort and overall. The duration (days) of exposure to treatment for each period will be calculated as date of last exposure to treatment – date of first dose + 1. The actual duration of treatment will be calculated as the exposure period – number of days on which treatment was temporarily stopped. The duration of exposure, average daily dose (mg), minimum daily dose (mg) and maximum daily dose (mg) for each period (as described in Section 7.2.1), and overall, as applicable will be summarized using descriptive statistics. Listings of exposure, drug interruptions and missed doses will also be presented.

7.3.2. Adverse Events

The verbatim terms as reported in the CRF by Investigators to identify AEs will be coded using MedDRA Version 22.0 or higher and summarized by primary SOC and PT.

Adverse event toxicity will be evaluated using the National Cancer Institute (NCI) Common Terminology Criteria for Adverse Events (CTCAE) Version 5.0 (published 27 Nov 2017).

Adverse event causality is determined by the Investigator using the following assessment categories: unrelated, or related.

Treatment-emergent AEs are defined as those AEs with onset on or after the first dose of treatment (ie, study drug). Events reported with a partial onset date (eg, month and year are reported but the day is missing) will be considered to be treatment-emergent if it cannot be confirmed that the event onset was prior to the first dose of study drug based on the available date entries.

7.3.2.1. Overall Summary of Adverse Events

An overall summary of TEAEs will be presented, including number of events and number and percentage of participants experiencing AEs. Percentage will be calculated as $n/N*100$, where n is the number of participants with events and N is the number of participants in the Safety Set. The summary will include categories indicating how many events are TEAEs, treatment-emergent SAEs, and treatment-emergent non-SAEs. Within TEAEs, the following subcategories will also be summarized:

- Toxicity of TEAEs (Grade 1 through Grade 5)
- Related TEAEs (not related, related)
- TEAEs leading to withdrawal of study drug
- TEAEs leading to withdrawal from the study
- TEAEs leading to death

A summary of events (E) and number of participants with events (n, %) for pre-treatment emergent events (PTAEs) will also be included with its relevant subcategories.

A listing of all TEAEs by participant will be presented. Separate listings will be produced for SAEs, AEs leading to study drug withdrawal, AEs resulting in death, AEs leading to withdrawal from the study and PTAEs.

7.3.2.2. Adverse Events and Serious Adverse Events by System Organ Class and Preferred Term

The number of TEAEs and the number and percentage of participants with events will be presented by SOC and PT. Participants are counted once in each SOC and PT. Percentages will be based on the Safety Set. The SOCs will be listed in alphabetical order and PTs within each SOC will be listed by descending frequency. If needed, terms will also be ordered alphabetically.

Treatment-emergent SAEs, treatment-emergent non-SAEs, TEAEs leading to withdrawal of study drug, TEAEs leading to withdrawal from the study, TEAEs leading to death, and PTAEs will be summarized using the same approach.

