9.4. Statistical Analyses

Statistical methods described in this section will be further elaborated in a separate Statistical Analysis Plan (SAP). Summary statistics will be computed and displayed by visit where applicable and will be presented by cohort (treatment experienced/treatment naïve), and overall Descriptive statistics for continuous variables will minimally include the number of participants, mean, standard deviation, minimum, median, and maximum. For categorical variables, frequencies, and percentages will be presented. Graphical displays will be provided as appropriate.

Analyses will be performed using the SAS® software Version 9.4 or higher.

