9.4.3. Safety Analysis

Safety analyses will be performed using the Safety Analysis Set.

Safety analyses will include all AEs, ECGs, clinical laboratory data, physical examinations, and vital sign measurements using descriptive statistics.

No inferential statistical analyses are planned for the safety parameters of this study. The incidence of AEs and SAEs will be summarized by System Organ Class and Preferred Term for each treatment and overall, and by relationship to study intervention. Adverse events will also be summarized by treatment and overall by severity. Serious AEs and AEs resulting in withdrawal from the study will be listed. Participants having multiple AEs within a category (eg, overall, System Organ Class, Preferred Term) will be counted once in that category. For severity tables, a participant's most severe event within a category will be counted.

Changes from baseline in vital sign measurements and laboratory assessments (eg, chemistry, hematology, coagulation, and urinalysis) will be summarized by treatment. Laboratory parameter values will be graded according to the National Cancer Institute Common Terminology Criteria for Adverse Events (CTCAE). Shift tables by treatment will be produced for these laboratory

parameters. These tables will summarize the number of participants with each baseline grade relative to the reference ranges and changes to the worst highest grade assessed post dose during the study.

Electrocardiogram parameters will be measured at the specified time points as per the SoA (Table 1), including heart rate, PR, RR, QRS, QT, and QTcF intervals. The average of the triplicate ECG readings at the time points collected will be calculated, and changes from pretreatment baseline values will be assessed by each treatment.

All concomitant medications will be coded and summarized using the World Health Organization (WHO) Drug Dictionary.

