Plasma concentrations of total molybdenum and PUF molybdenum vs. time data will be presented in a data listing by participant. Plasma concentration data will be summarized separately by analyte and time point for each treatment by day using the following descriptive statistics: number of participants, arithmetic mean, geometric mean (GM), SD, coefficient of variation (CV), GMCV, median, minimum, and maximum. Mean plasma concentration versus scheduled time profiles will be presented in figures on both linear and semilogarithmic scales. Individual plasma concentration versus actual time profiles will be presented similarly.

Pharmacokinetic parameters derived from plasma concentrations of total molybdenum and PUF molybdenum will be presented in data listings and summarized separately using the following descriptive statistics: number of participants, arithmetic mean, GM, SD, arithmetic CV, GMCV, median, minimum, and maximum. Geometric mean and geometric CV will be presented for C_{\max} and AUCs only.

For PD (total and PUF copper and LBC) and biomarker endpoints (ceruloplasmin, ceruloplasmin-bound copper), concentration-time data will be listed and summarized with descriptive statistics and plotted. The same analyses will be conducted on the absolute and percent changes from baseline of these concentration-time data.

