7.3.3.2. Vital Signs

Changes from Baseline in vital signs (blood pressure, heart rate, respiratory rate, and body temperature) at each visit will be summarized descriptively by cohort and overall. Missing vital signs data will not be imputed and only scheduled assessments will be summarized in tables; unscheduled assessments will be presented in data listings. A listing of vital signs will be presented by participant, cohort, vital sign, and visit.

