7.4. Pharmacokinetic and Pharmacodynamic Analyses

For PK and PD endpoints, analyses will be performed using the PK and PD Analysis Sets respectively. The PK and PD concentration and parameters, as data permit, will be summarized by cohort.

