7.4.1. Pharmacokinetic Concentration Analyses

Plasma concentrations of total molybdenum and PUF molybdenum (as surrogate measures of ALXN1840 PK) vs. time data will be presented in a data listing by participant. Plasma concentration data will be summarized separately by analyte, treatment (dose), day, and time point using the following descriptive statistics: number of participants, arithmetic mean, SD, coefficient of variation (CV), geometric mean (GM), GMCV, 95% confidence interval (CI), median, minimum, and maximum. When calculating the geometric mean, values of 0 will be discarded. For summary statistic calculations, plasma concentration values below the lower limit of quantification (LLOQ) will be set to the LLOQ for analyses using the Full Analysis Set and will be set to 0 for analyses using the PK Analysis Set.

Mean plasma concentration versus scheduled time profiles will be presented in figures on both linear and semilogarithmic scales. Individual plasma concentration versus actual time profiles will be presented similarly. The time to reach steady state will be graphically assessed by plotting mean plasma trough (pre-dose) concentration observed at the start of the dosing interval (C_{trough}) versus study day in both linear and semilogarithmic scales.

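### After an outpatient extension of 9 to 14 days the SAP summarizes 15 mg vital signs as Day 40; separately, its adverse event tables have no split by dose, which the protocol's undefined by-treatment wording may call for

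*SAP*

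**What the plan says.** **Visits.** SAP 9.2.3 counts days by calendar from first dose, and SAP 9.2.8 uses those actual days to place data in visit windows. Its Table 3 gives the vital-sign windows: Days 2 to 15 for Day 9, Days 16 to 31 for Day 23, and Day 32 onward for Day 40. If several values share a window, the one nearest the target day is summarized. Other data follow the same rule on their own schedules. Protocol 4.1 and its Table 4 allow up to 14 extra outpatient days; dosing continues, the actual length is recorded, and the participant re-enters at nominal Day 23. By protocol 1.2 the dose is 15 mg through Day 28 and 30 mg from Day 29.

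**Adverse events.** Protocol 9.4.3 states "The incidence of AEs and SAEs will be summarized by System Organ Class and Preferred Term for each treatment and overall" and "Adverse events will also be summarized by treatment and overall by severity". SAP 7.3.2.1 uses the whole Safety Set as denominator. SAP 7.3.2.2 says "Percentages will be based on the Safety Set", and 7.3.2.5 refers back to it. SAP 7.3.2.3 and 7.3.2.4 use those treated in the *treatment cohort*; the only cohorts defined are treatment-experienced and treatment-naïve. SAP 7.3.2.6 names no dose split. SAP 7.3.2 and 9.2.1 classify an event only as before, or on or after, first dose. SAP 4.1 declares no change from the protocol.

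**The concern.** The study doubles the dose within each participant, and the safety objective names both 15 mg/day and 30 mg/day. A safety summary should therefore not file a value measured on one dose under a visit that stands for the other. The windowing rule does so for some participants, and it leaves their 30 mg value out of the table.

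The adverse event tables raise a softer question. If *treatment* in protocol 9.4.3 means dose, the SAP omits a planned split without saying so. Whatever the word means, a reader who wants the experience at 30 mg has to rebuild it from listings. These are interim outputs to support regulatory submissions (SAP 4), taken at a data cut (SAP 6), possibly before everyone completes treatment (protocol 9.5). Some participants may also stay on 15 mg (protocol Table 4). The number exposed to 30 mg may then be smaller than the Safety Set.

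**Working it through.** **1. Visit windows.** First the SAP's own boundary: the Day 40 lower bound is ceiling(40 − (40 − 23)/2) = ceiling(31.5) = 32, as in Table 3.

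Let *e* be the extension in days, 0 to 14.
- Nominal Day 23 is actual Day 23 + *e*. It enters the Day 40 window when 23 + *e* ≥ 32, that is *e* ≥ 9. Its distance from Day 40 is then 17 − *e*.
- Nominal Day 40 is actual Day 40 + *e*, at distance *e*.
- The End of Study visit (nominal Day 54) is at distance 14 + *e*.
- Nominal Day 23 is nearer than nominal Day 40 when 17 − *e* < *e*, that is *e* > 8.5.

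| *e* | Nominal Day 23: actual day (distance) | Nominal Day 40: actual day (distance) | End of Study: distance | Summarized as Day 40 |
|---|---|---|---|---|
| 0 | 23 (Day 23 window) | 40 (0) | 14 | nominal Day 40 |
| 8 | 31 (Day 23 window) | 48 (8) | 22 | nominal Day 40 |
| 9 | 32 (8) | 49 (9) | 23 | nominal Day 23 |
| 14 | 37 (3) | 54 (14) | 28 | nominal Day 23 |

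So for every extension from 9 to 14 days the nominal Day 23 value is the one summarized. On the Table 3 schedule, the same participant then has no scheduled vital signs in the Day 23 window.

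**2. What *treatment* means in protocol 9.4.3.** No passage defines it. The evidence divides as follows.

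- For dose: protocol 9.4.4 writes "Plasma concentration data will be summarized separately by analyte and time point for each treatment by day", the SAP's matching sentence reads "summarized separately by analyte, treatment (dose), day, and time point", and SAP 7.4 names the other grouping separately: "The PK and PD concentration and parameters, as data permit, will be summarized by cohort". The protocol has its own word, *cohort*, for prior-therapy groups. The safety objective names both doses. SAP 7.3.3.1 keeps laboratory shift tables by treatment beside laboratory changes by cohort.
- For cohort: protocol 9.4 sets the general display, "Summary statistics will be computed and displayed by visit where applicable and will be presented by cohort". Protocol 9.4.3 also plans vital-sign and laboratory changes by treatment, and the SAP gives both by cohort. For vital signs, changes "at each visit will be summarized descriptively by cohort and overall". SAP 7.3.2.3 and 7.3.2.4 speak of a *treatment cohort*.

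**3. Size for adverse events.** Assumption: 10 participants dosed, of whom *k* reached 30 mg by the data cut. The documents give no *k*. One participant with an event on 30 mg is 1/10 = 10.0% of the Safety Set, but 1/8 = 12.5% (*k* = 8) or 1/5 = 20.0% (*k* = 5) of those exposed. With no events, the one-sided 95% exact upper limit 1 − 0.05^(1/*n*) is 25.9% for *n* = 10, 31.2% for 8 and 45.1% for 5. These limits only illustrate how much an absence of events can say; the plan has no inferential safety analysis.

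**4. Exposure is uneven.** With full titration and a last dose on Day 39, there are 28 days at 15 mg and 39 − 28 = 11 at 30 mg, so 15 mg has 28/39 = 71.8% of dosing days. With a 14-day extension this is 42/53 = 79.2%. If the 40 days in protocol Table 6 put the last dose on Day 40, the shares are 28/40 = 70.0% and 42/54 = 77.8%. Event counts by dose therefore need participant-days beside them.

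**The case against.** **On windowing.** The extension is optional, and the fault appears only at 9 to 14 days. SAP 9.2.8 keeps the reported visit label and the study day in the listings, so a careful reader could find the reassignment. Both points are true. The summary table would still be wrong for that participant. Only the vital-sign windows were worked through here.

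**On adverse events.** A reader might infer that the SAP has dropped a dose analysis the protocol promised, and that SAP 4.1 is therefore false. The documents do not establish that. *Treatment* is undefined in this single-arm study, and the SAP renders other by-treatment items of the same protocol section by cohort. On that reading the SAP largely matches the protocol.

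A reader might also infer that the Safety Set is the wrong denominator. It is the right one for what the tables report, which is incidence among all treated participants.

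Much of the information is planned elsewhere: participant listings of events, and exposure and daily dose by period (SAP 7.3.1). With about 10 participants, SAP 7 allows listings alone. The fixed order of doses also confounds dose with time. Protocol Table 3 places transaminase elevations usually at 3 to 6 weeks, about Days 21 to 42, which straddles Day 29. By-dose tables could describe but not attribute. All of this stands; it limits the adverse event part to an improvement.

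**On exposure.** Footnote e of the Schedule of Activities might suggest 30 mg dosing up to Day 54. The Schedule marks 30 mg only to Day 39, and under protocol 6.7 participants after Day 40 move to other therapy or may request preapproval access. No Day 54 exposure figure is supported.

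**Conclusion.** Two conclusions of different weight.

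1. The windowing rule is wrong as written for extensions of 9 to 14 days. It reports a 15 mg vital-sign value as Day 40 and leaves out the true Day 40 value. This follows from the SAP's own rule and does not depend on what *treatment* means. That the omitted value reflects 30 mg assumes the participant was titrated. How many participants are affected depends on how many extensions are that long, which the documents cannot tell us.

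2. By-dose adverse event tables are a cheap improvement that serves the stated safety objective. Dose is a well-supported reading of protocol 9.4.3, but it is not proven. The pooled percentage is correct for overall incidence; it does not give a 30 mg rate when fewer participants reach 30 mg. The 12.5% and 20.0% figures rest on assumed numbers exposed.

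Neither part affects the primary endpoint.

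**What to change.** - **SAP 9.2.8:** for participants with an extension, window on the nominal visit, or subtract the recorded extension from the actual day. Apply the same correction to other by-visit data that use this rule. The extension length is already recorded, so the cost is a line of SAP text and a small programming change.
- **SAP 7.3.2:** assign each treatment-emergent event to the dose actually taken at onset. Show events during interruptions and after the actual last dose separately. Add by-dose columns to the SOC/PT and severity tables, with participants exposed and participant-days at each dose. Keep the pooled and cohort displays. Label the new columns descriptive and confounded with time on treatment. Onset and dosing dates are already collected. The cost is SAP wording and extra columns; the downside is sparse cells with about 10 participants.
- **If the sponsor means cohort:** say so in the SAP. If dose was meant but will not be shown, disclose and justify the departure in SAP 4.1.
- **End of dosing:** the passages on when dosing ends must be reconciled (Day 39 in protocol 1.2, 40 days in Table 6, Day 54 in footnote e of Table 1, and section 6.7), because the group for events after the last dose depends on them.

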7.3.2.3. Adverse Events by System Organ Class

The number of TEAEs and the number and percentage of participants with events will be presented by SOC. Participants are counted once in each SOC only. Percentages will be based on the total number of treated participants in the treatment cohort.

7.3.2.4. Adverse Events by Preferred Term

The number of TEAEs and the number and percentage of participants with events will be presented by PT. Participants are counted once in each PT only. Percentages will be based on the total number of treated participants in the treatment cohort.

7.3.2.5. Adverse Events and Serious Adverse Events by System Organ Class, Preferred Term, and Relationship

The number of TEAEs and the number and percentage of participants with events will be presented by SOC and PT as described in Section 7.3.2.2 by relationship (related, not related). If a participant has more than one occurrence of an AE, the strongest relationship to study treatment will be used in the summary table. If relationship to study drug is missing, the AE will be assumed to be related. A similar analysis will be conducted for treatment-emergent SAEs.

The number of related TEAEs and the number and percentage of participants with related TEAEs will be summarized by SOC and PT, and separately by PT only. The same analyses will be produced for related treatment-emergent SAEs.

Lastly, the number of TEAEs by SOC, PT and relationship, without taking into account the highest relationship, will be analyzed. A similar analysis will be conducted for treatment-emergent SAEs.

7.3.2.6. Adverse Events and Serious Adverse Events by System Organ Class, Preferred Term, and Toxicity

The number of TEAEs and the number and percentage of participants with events will be presented by SOC, PT and toxicity (ie, CTCAE grade). If a participant has more than one occurrence of an AE, the highest toxicity reported will be used. The number of TEAEs by SOC, PT and toxicity, without taking into account the highest toxicity, will also be analyzed.

Additionally, a summary of related TEAEs by SOC, PT and toxicity using the highest toxicity will be presented.

7.3.3. Other Safety

7.3.3.1. Analyses for Laboratory Tests

Actual values and changes from treatment Baseline will be summarized descriptively for participants with available data for each laboratory parameter by cohort and overall. Missing laboratory data will not be imputed and only scheduled assessments will be included in by-visit summaries. All data, including that which is only collected at Screening, will be included in data listings. Laboratory measurements will be listed separately by participant, laboratory test, unit, and visit.

Laboratory parameter values will be graded according to the National Cancer Institute Common Terminology Criteria for Adverse Events (CTCAE). Shift tables by treatment will be produced for these laboratory parameters. These tables will summarize the number of participants with each baseline grade relative to the reference ranges and changes to the worst highest grade assessed post dose during the study.

Summary results for shift will include the count and percentage of participants within each shift category by scheduled visit. Laboratory values outside the normal range will also be summarized and assessed for trends indicating a safety signal. Additionally, a summary and listing of liver enzyme elevation will be presented and an evaluation of drug-induced serious hepatotoxicity plot will be created.

7.3.3.2. Vital Signs

Changes from Baseline in vital signs (blood pressure, heart rate, respiratory rate, and body temperature) at each visit will be summarized descriptively by cohort and overall. Missing vital signs data will not be imputed and only scheduled assessments will be summarized in tables; unscheduled assessments will be presented in data listings. A listing of vital signs will be presented by participant, cohort, vital sign, and visit.

